9.4 Variables

The following variables will be collected for assessments over the course of the study.

9.4.1 Exposure Assessment

Opioid and non-opioid treatments will be assessed using ATC and PZN codes (see Table 9-1) as described below:

- **Opioid Treatment** received between January 1st 2012 and December 31st 2016 in at least 3 quarters, over a 60-month period based on ATC code N02A%.
- **Non-Opioid Treatment** (NSAIDs, anticonvulsants, antidepressants) received between January 1st 2012 and December 31st 2016 in at least 3 quarters, over a 60-month period, based on ATC code in Table 9-1.
- **Treatment Dosage** will be assessed based on DDD assessment per ATC code using DIMDI data. Dosage will thus be calculated as medication dose per day based on the average prescription per year of the year. The number of medication claims, the number of drug packages and DDD per package are used to estimate the daily dose.

- Treatment dosage of opioid treatment will be defined based on morphine equivalence. The low dosage is thus defined as less than 60mg/d morphine equivalence. The intermediate dosage will be defined as a dosage between 60mg/d and 120mg/d morphine equivalence. The high dosage will be defined as 120mg/d morphine equivalence or higher.
- Treatment dosage for non-opioid treatment is defined as follows:
 - Anticonvulsive: based on gabapentin equivalence. The low dosage is thus defined as a daily dosage of less than 600mg/d gabapentin equivalents and a high dosage of 600mg/d or more gabapentin equivalents.
 - Antidepressants: via standard psychiatric dose according to AKDÄ (2006) recommendations: daily doses below the minimum standard psychiatric dose will be defined as "low", dosages above as "high". The standard psychiatric dose per ATC can be seen in Table 9-5.

Table 9-5:: Standard psychiatric doses as threshold for low/high dosage

Active substance	ATC code	Minimum standard psychiatric dose
Amitriptylin	N06AA09	100
Amitriptylinoxid	N06AA09	100
Clomipramin	N06AA04	100
Desipramin	N06AA01	100
Dibenzepin	N06AA08	240
Doxepin	N06AA12	100
Imipramin	N06AA02	100
Maprotilin	N06AA21	100
Nortriptylin	N06AA10	50

Trimipramin	N06AA06	100
Citalopram	N06AB04	20
Escitalopram	N06AB10	10
Fluoxetin	N06AB03	20
Fluvoxamin	N06AB08	100
Paroxetin	N06AB05	20
Sertralin	N06AB06	50
Moclobemid	N06AG02	300
Tranylcypromin	N06AF04	20
Venlafaxin	N06AX16	75
Duloxetin	N06AX21	60
Reboxetin	N06AX18	8
Mianserin	N06AX03	60
Mirtazapin	N06AX11	15
Trazodon	N06AX05	200

- **Duration of treatment** will be operationalized as time in months between the last and first prescription of an opioid or non-opioid treatment between 01.01.2013 and 31.12.2017. Duration might endure at least 9 months because 3 quarters of prescription are the inclusion criterion. The duration of treatment might be 60 months as a Maximum (5 years of exposure time).

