9.1 Study Design

This is a retrospective observational cohort study based on an anonymized German health claims database. This database contains data on around 4 million insured people from 69 German statutory health insurances (SHI). This research database is a complete, longitudinal claims dataset of approx. 7 million individual patients (ca. 10% of the statutory insured population of Germany) between 2012 and 2017. The analyses for this study will be done on a 4 million patients subset that is stratified by age

and gender based on the 2013 population structure of Germany as reported by the German Federal Statistical Office DeStatis.

This study consists of two cohorts: opioid and non-opioid patients. Only patients who started their therapy between 2013 and 2017 and had no therapy in 2012 (therapy naïve patients) will be included in the study.

Exposure time is defined as max. 5 years after the initial prescription for each patient, so that exposure time is max. 60 months per patient.

Exposure time may end before the end of study if patient died, stopped treatment (end of follow-up after 1 year without treatment with opioids / other pain medication), changed treatment group (from opioids to other pain medication or vice versa) or was lost to follow up due to other reasons (e.g. change of insurance), whichever occurs first.

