9.2.1 Study Period

Due to data protection regulations in Germany, only an extract of maximum 6 years of data coverage could be available for the research purposes: 1st January 2012 to 31st December 2017.

The **baseline period** is defined as the period prior to the date of first diagnosis of diagnoses or first opioid or non-opioid treatment initiation as described in inclusion criteria (Chapter 9.2.2.1). The baseline assessment period endures between January 01, 2012 and first study medication prescription.

Index treatment is defined as the date of first opioid or non-opioid treatment prescription between 1st January 2013 and 31st December 2017.

Exposure time is defined as time between index treatment and December 31, 2017. Considering data availability of a maximum of 6 years and prescription in a required time period of 60 months, exposure time endures maximum five years. Thus, patients can be censored at death (death date in the linked records), last known record for the patient in the German health claims database, switching of treatment groups (from opioid group to non-opioid group or vice versa), 12 months without opioid/non-opioid treatment or 31st December 2017 (end of latest data cut), whichever comes first.

[figure not shown]
The **outcomes** will be assessed between index treatment and 31.12.2017.

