9.2.2 Patient Eligibility

9.2.2.1 Inclusion Criteria

For the purposes of this study, the requested extraction of the database consists of population of patients with chronic non-cancer pain corresponding to the following criteria. Inclusion and exclusion criteria are also provided in Figure 2.

Figure 2: Inclusion and exclusion criteria

Cohort A

- Patients are included in the long-term opioid group if they started an opioid-therapy between 2013 and 2017 and received consecutive prescriptions for opioid medications over a minimum of 3 quarters, over a 60-month period between January 1, 2013, and December 31, 2017. The treatment will be assessed using the ATC codes of opioid treatment N02AA01, N02AA05, N02AB03, N02AE01, N02AX02, N02AX01, N02AX06 (see also Table 9-1) reported in reimbursed medicines to patients.

- Patients are only included if they have been diagnosed in at least three quarters in the study period with one of the following diagnoses: R51, R52*, M00*-M99*, G43*-G44*, G50.0 or G50.1, F45.4*, G62*, or E10.4*-E14.4 plus G63.3. At least one diagnoses must be between 1 January 2012 and index treatment and main and secondary hospital diagnoses (*i.e. Haupt- und Nebendiagnosen*) will be used to include the patients.

Cohort B

- Patients with non-opioid pain medication are included, if they received a medication therapy with anticonvulsants (gabapentin, pregabalin, carbamazepine), antidepressants or non-opioid analgesics (NSAIDs, Metamizole) over a minimum of 3 quarters, over a 60-month period between January 1, 2013, and December 31, 2017. The non-opioid treatment will be assessed using the ATC codes (N03AX12, N03AX16, N03AF01, see also Table 9-1) of treatment reported in reimbursed medicines to patients.
- Patients are only included if they have been diagnosed in at least three quarters in 2012 with one of the following diagnoses: R51, R52*, M00*-M99*, G43*-G44*, G50.0 or G50.1, F45.4*, G62*, or E10.4*-E14.4 plus G63.3. At least one diagnoses must be between 1 January 2012 and index treatment and main and secondary hospital diagnoses (*i.e. Haupt- und Nebendiagnosen*) will be used to include the patients.

All diagnoses that lead to patient inclusion when coded between 01.01.2012 and index treatment and in at least three quarters within the study period are provided in Table 9-2 below.

Table 9-1: List of ATC codes of study opioid and non-opioids

Name	ATC Code
Study opioids	
Morphine	N02AA01
Oxycodone	N02AA05
Fentanyl	N02AB03

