9.3.2 Other risk adjustment

The following Cox proportional hazards time to event regression model describes the method of another risk adjustment:

$$\lambda(tX_j) = \lambda_0(t) * \exp(\beta_1 X_{j1} + \beta_2 X_{j2} + \dots + \beta_m X_{jm})$$

This expression gives the hazard rate at time t for person j

- $\lambda(tX_j)$ is the hazard for outcome at time t for person j
- where \exp is a mathematical constant, Euler's number ($e = 2,71828$)
- X_1, \dots, X_m are the values of exposure variables and covariates
- β_1, \dots, β_m are estimated regression coefficients that indicate the importance of exposure variables and covariates.
- $\lambda_0(t)$ is the baseline hazard indicating hazard for the outcome if all exposure variables are zero (similar meaning "intercept").

Following covariates will be used in the Cox proportional hazards time to event regression:

- **Gender** (sex – male, female) will be assessed via indicated sex in the social insurance register

¹¹ Ray et al., 2016

- **Age** will be assessed using national insurance data by date of birth and calculated based on the 'index treatment' (the date of first study medication claim between 1st January 2012 and 31st December 2017).
- **Charlson Comorbidity Index (CCI)** will base on the the modified CCI according to Quan (2005) and Quan (2011). Using modified CCI is preferable because it was validated by ICD-10 while, for example, the Romano-CCI was validated using ICD-9¹². The modified CCI predicts the one-year mortality for a patient who may have a range of comorbid conditions (e.g. AIDS, or cancer) with a total of 16 conditions¹³. Each condition is assigned a score between 0 (no risk) and 6 (high risk), depending on the risk of dying associated with conditions. Age and gender are defined as hazard ratios. The scores are summed up to provide a total score to predict mortality. CCI will be added as a covariate in the Cox regression model (Table 9-4).
- **Duration of the opioid /non-opioid treatment** will be used as a one of the predictors of opioid treatment in be added as a covariate in the Cox regression model and assessed as the difference between the last opioid or non-opioid prescription based on ATC codes and the first opioid or non-opioid prescription in months, between January 1st 2012 and December 31st 2016. The prescription will be dummy coded as 1 (prescription available) or 0 (no prescription available).

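### Treatment duration is measured in a fixed calendar window and not cut at the patient's own censoring date, so it can include months after follow-up has ended.

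*Protocol*

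**What the plan says.** Protocol 9.4.1 operationalizes duration as "time in months between the last and first prescription of an opioid or non-opioid treatment between 01.01.2013 and 31.12.2017". It adds "The duration of treatment might be 60 months as a Maximum (5 years of exposure time" and "Duration might endure at least 9 months because 3 quarters of prescription are the inclusion criterion".

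Protocol 9.3.2 lists duration among the Cox covariates, "assessed as the difference between the last opioid or non-opioid prescription based on ATC codes and the first opioid or non-opioid prescription in months", here with a window from January 2012 to December 2016. The paragraph after Table 9-4 says that covariates other than dosage are not time-varying, so duration enters as one fixed value per patient.

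The end of follow-up is set elsewhere and patient by patient. Protocol 9.1 ends exposure time when the patient "stopped treatment (end of follow-up after 1 year without treatment with opioids / other pain medication), changed treatment group". Protocol 9.2.1 lists as censoring events "switching of treatment groups (from opioid group to non-opioid group or vice versa), 12 months without opioid/non-opioid treatment or 31st December 2017". The Follow-up paragraph of the Protocol's summary gives the same two events. No exclusion criterion in 9.2.2.2 removes patients who later switch or restart.

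**The concern.** The duration rule and the censoring rule do not fit together. Duration is bounded only by calendar dates, whereas follow-up stops at patient-specific events. Applied as written, the rule looks past the censoring date to the last claim in the window and counts everything in between as treatment, whether the patient was untreated or on the other treatment.

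Two things are at stake. First, any description of how long the long-term opioid and non-opioid cohorts were treated would be too long, by an amount that depends on restarting and switching, which may differ between cohorts. Second, the covariate in 9.3.2 would use prescriptions issued after the patient had left the risk set.

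**Working it through.** **Inputs.** Window 01.01.2013 to 31.12.2017 (9.4.1); window ending 31.12.2016 (9.3.2); censoring at a switch or after 12 months without treatment (9.1, 9.2.1). The Protocol gives no distribution of stops or switches, so the patient histories are assumptions. Months are days / 30.4375.

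**The Protocol's own figures.** Maximum: 01.01.2013 to 31.12.2017 is 1825 days, and 1825 / 30.4375 = 59.96, so the stated 60 months reproduces. Minimum: the stated 9 months does not. Claims in three consecutive quarters can lie as close as 31 March to 1 July (92 days, 3.0 months) and at most 1 January to 30 September (272 days, 8.9 months). That is a separate slip in the same paragraph.

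**Formulas.**
- Own follow-up = index to the switch date, or index to the last prescription before the gap plus 12 months.
- Duration as written = index to the last claim in the window. Claims are assumed to run to the end of the window.
- Ratio = duration / own follow-up.

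| History | Own follow-up, days (months) | Duration to 31.12.2017, days (months) | Ratio, 9.4.1 window | Ratio, window ending 31.12.2016 |
|---|---|---|---|---|
| Index 31.03.2013, stop at 3.0 months, restart | 457 (15.0) | 1736 (57.0) | 3.8 | 1371/457 = 3.0 |
| Index 01.01.2013, stop at 8.9 months, restart | 637 (20.9) | 1825 (60.0) | 2.9 | 1460/637 = 2.3 |
| Index 01.01.2013, stop at 24 months, restart | 1095 (36.0) | 1825 (60.0) | 1.7 | 1460/1095 = 1.3 |
| Index 01.01.2013, switch at 6 months | 182 (6.0) | 1825 (60.0) | 10.0 | 1460/182 = 8.0 |
| Index 01.01.2013, switch at 9 months | 273 (9.0) | 1825 (60.0) | 6.7 | 1460/273 = 5.3 |
| Index 01.01.2013, switch at 24 months | 730 (24.0) | 1825 (60.0) | 2.5 | 1460/730 = 2.0 |
| Index 01.01.2015, switch at 9 months | 273 (9.0) | 1095 (36.0) | 4.0 | 730/273 = 2.7 |

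**Which later claims count.** The stop-and-restart rows hold on any reading if the restart is in the original class. The switch rows hold on any reading for a patient who later returns to the original class and has claims to the end of the window. On the literal reading they also hold for one who simply stays on the new class.

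**With the cut.** If only prescriptions up to the patient's own censoring date count, the ratio cannot exceed 1. The 9-month switcher has at most 9.0 months instead of 60.0, and the patient who stops at 8.9 months has 8.9 instead of 60.0.

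**The two windows.** Patients had no study therapy in 2012, so the earlier start in 9.3.2 changes little; the earlier end does matter. Index treatment may fall in 2017 (9.2.1), and such a patient has no prescription inside the 9.3.2 window, so the covariate is undefined.

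**The case against.** The strongest objection is that an opioid or a non-opioid treatment means the drugs of the patient's own cohort, respectively. This is a fair reading: the Protocol's summary speaks of the two treatments respectively, and 9.4.1 defines them separately. Take an opioid patient treated 15.01.2013 to 15.09.2013 with one NSAID claim on 01.12.2017. Read literally, duration is 1781 days (58.5 months) against 8.0 months of opioid treatment, and a reader might infer a roughly sevenfold overstatement (1781/243 = 7.3). The documents do not support that as a general figure. On the respective reading duration is 8.0 months and there is no excess. Against follow-up, which ends at 20.0 months, even the literal ratio is 2.9 (1781/608). In the 9.3.2 window the 2017 claim drops out altogether. What survives is the patient who returns to the original class after a switch or a gap of more than 12 months, and the respective reading does nothing for that case.

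Second, the reference to 5 years of exposure time in 9.4.1 might imply that duration stays inside exposure time, which 9.1 ends at a stop or switch. But 9.2.1 opens by defining exposure time as index treatment to 31 December 2017, so the phrase explains the 60-month maximum and supplies no patient-level cut.

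Third, 9.4.2.1 omits switch and stop from the censoring list for the mortality rate, and against that person-time duration would not be too long. It would still count untreated or other-treatment months as treatment, and the summary, 9.1 and 9.2.1 do censor at both events.

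Fourth, derivation detail can be left to a statistical analysis plan. Here, however, the Protocol fixes the rule itself, twice and with different windows.

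The objection that duration is neither an objective nor an endpoint stands, and it limits how much weight the point can carry.

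**Conclusion.** The point holds as a mismatch between a stated exposure definition and the stated censoring rules. It certainly applies to patients who return to their own class after censoring. Whether it also applies to patients with later claims of the other class depends on an ambiguous phrase.

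Under the 9.4.1 window the illustrative excess over own follow-up is about 1.7- to 3.8-fold after stop and restart, and about 2.5- to 10-fold after a switch at 6 to 24 months. It is smaller under the 9.3.2 window. These figures assume claims up to the end of the window and show what the rule permits, not what is typical. The Protocol gives nothing from which to estimate the share of patients affected.

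A reader might also infer that the mortality hazard ratio is biased by a known amount. The documents do not allow that: no size or direction can be derived. The death endpoint itself is untouched; the affected items are a described exposure variable and one listed covariate.

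**What to change.** Use the same definition and one reconciled window in 9.4.1 and 9.3.2: time from the index prescription to the last prescription of the patient's own cohort's drugs on or before that patient's censoring date (switch, 12 months without treatment, death, end of insurance or 31.12.2017). State the cohort restriction explicitly, and correct the 9-month minimum in the same edit.

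The cost is one sentence in each of two sections and a filter in the derivation program, with no new data. The change corrects the described duration and removes post-censoring information from the covariate. It does not resolve the separate problem that duration, even when cut at censoring, is known only after baseline and is shortened by death, so that as a fixed Cox covariate it depends on survival. That needs its own decision.

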9.4.2 Outcome Assessment

The study will assess the following main outcomes during the follow-up period.

9.4.2.1 Primary endpoint

Primary endpoint is **death** by any course in the study follow-up. Death will be assessed during the follow-up period by number of patients who deceased during follow-up period (2013 – 2017) via the date of death in German claims data base. Additionally, mortality rate will be estimated as number of patients who died during the follow-up divided by person-time

of follow-up, censoring at time of death, last known record for the patient in the database, or 31st December 2017 (end of latest data cut), whichever is earlier.

9.4.2.2 Secondary endpoints

Secondary endpoints are following:

- **Hospitalization due to any course.** Hospitalization will be assessed via the number of hospitalisations (calculated by counting the number of discharge dates (KH_Fall. Entlassungsdatum) in the year of interest, hospitalization rate, and length of stay in the hospital (KH_Fall. Verweildauer). The rate of hospitalization will be estimated as the number of patients with at least one hospitalization during the follow-up period divided by person-time of follow-up, censoring at time of death, last known record for the patient in the database, or 31st December 2017 (end of latest data cut), whichever is earlier.
- **Intensive care unit (ICU-stay)** stay is defined as patient's stay based on specialty of department in hospital (KH_OPS.Fachabteilung = 3600).
- **Hospitalization with to misuse or addiction.** The hospitalization with misuse or addiction will be analysed, if principal (main) diagnosis at discharge date between January 1st 2013 and December 31st 2017 contains at least one ICD-10 diagnosis of misuse/addiction: F10* or F11* or F13* or F19* or T40* (see also Appendix B in **Fehler! Verweisquelle konnte nicht gefunden werden.**).
- **Hospital admission diagnoses.** We report the hospital admission diagnoses based on ICD-10 codes between January 1st 2013 and December 31st 2017.
- **Coding of procedures in hospitals** that indicate number of patients that were hospitalized with severe diseases such as cardiovascular

diseases will be assessed via OPS-Codes provided in Appendix B as an excelsheet.

- **Coding of a misuse or addiction diagnosis in the outpatient sector** will be assessed via number of codings of misuse/addiction (ICD Codes = F10* or F11* or F13* or F19* or T40*) in outpatient sector by general practitioner or a specialist (e.g. psychiatrist), as ensured diagnosis (Diagnosesicherheit='G'). Additionally, the number of patients with a least one coding of ICD 10 codes of an ensured misuse/addiction in outpatient sector by general practitioner or a specialist (e.g. psychiatrist) will be assessed.
- **Sick leave** will be assessed as an absolute number and relative frequencies of patients with an attest of inability to work (patients with attest of inability to work as a percentage of all patients) in 2013-2017 and number of days being off work.
- **Hospital deaths** will be assessed via reason of discharge = death (Entlassgrund = Tod)
- **Main- and secondary discharge diagnoses** from hospital deaths will be assessed as the TOP 20 diagnoses of patients who deceased during a hospital stay

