9.2 Setting and Study Population

The database contains data on around 4 million insured people from 69 German statutory health insurances (SHI). German SHI system comprises of approximately 120 independent health insurance companies. Funds paid by these SHI to any provider of health care (e.g. hospitals, physicians, pharmacies, psychotherapists and physiotherapists) represent almost the complete picture of the total health care costs of individual patients. All health insurance data can be linked to patients' demographics including age and gender. Health care data in the database include:

- Patient demographics:
 - age
 - gender
 - date of death

- region of residence
- insurance status
- date of insurance start and end
- Hospital care:
 - main diagnosis (ICD-10-GM codes) and additional diagnoses
 - procedures and surgeries
 - date of hospital admission
 - reason for admission (e.g. accident, emergency, normal)
 - date of end of hospital stay
 - reason of end of hospital stay (e.g. regular discharge from hospital, death)
 - DRG-Code
 - costs
- Outpatient care:
 - diagnoses (ICD-10-GM codes)
 - quarter in which the diagnosis was documented
 - procedures performed (EBM codes, e.g. laboratory tests, radiology, echocardiography) and date of procedure
 - type of specialist that documented the diagnosis and performed the procedure (e.g. cardiologist, general practitioner)
 - costs
- Pharmaceutical claims:

- drug dispensed (PZN code, which identifies medications at the package level) – this is mapped to ATC codes and DDDs
- quantity dispensed
- day of prescription
- day of dispensing
- type of specialist prescribing the medication (e.g. general practitioner)
- costs of drugs dispensed from the perspective of the statutory health insurance (without individual rebates between insurance and pharmaceutical companies)
- Physical therapy and technical aids:
 - type of therapy (e.g. massage, occupational therapy, walker, wheel chair)
 - quantity prescribed
 - type of care provider
 - start and end date
 - costs
- Sick leave:
 - diagnoses that cause sick leave
 - duration of sick leave
 - start date of sick leave
 - end date of sick leave

- type of specialist that filled out the sick leave form (e.g. general practitioner)
- costs of sick leave

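### Hospital stays are dated by discharge, so a stay that began before the first study prescription and ended on or after it counts as an outcome of treatment

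*Protocol*

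**What the plan says.** Four parts of the protocol bear on this.

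- **Counting rule (9.4.2.2).** The number of hospitalisations is "calculated by counting the number of discharge dates (KH_Fall. Entlassungsdatum) in the year of interest". Length of stay is taken from the database field, "length of stay in the hospital (KH_Fall. Verweildauer", and no cut at index or at the end of follow-up is stated.
- **Misuse or addiction stay (9.4.2.2).** It is identified from the "principal (main) diagnosis at discharge date between January 1st 2013 and December 31st 2017". This is also discharge dating, in a calendar window that does not mention the patient's index date.
- **Time zero and outcome window (9.2.1).** "Index treatment is defined as the date of first opioid or non-opioid treatment prescription", and outcomes "will be assessed between index treatment and 31.12.2017", subject to earlier censoring.
- **Data available (9.2).** The hospital data include the "date of hospital admission" as well as the date the stay ended.

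The hospitalisation rate is a separate measure and has no dating rule of its own: "The rate of hospitalization will be estimated as the number of patients with at least one hospitalization during the follow-up period divided by person-time". The secondary objective (section 8.2) is framed in terms of hospital admissions.

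**The concern.** The event that the secondary objective is about is the admission, but the date that decides whether it counts is the discharge. For most stays the difference does not matter. It matters for a stay in progress at the index prescription or ending on that day: the admission came before the treatment, and may even be the reason for it, yet the stay is credited to that treatment. Its whole recorded length goes with it and, for the misuse endpoint, so does its principal diagnosis.

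These events are in the wrong time order for a comparison of treatment effects. If they are equally common in both cohorts, they inflate both counts and pull the ratio slightly towards 1 when there is a true difference. If one cohort starts treatment around a hospital stay more often, they create a difference where none exists. Section 9.10.1.2 presents hospitalisation as one of two key outcomes less prone to bias, so the rule that dates it should not add avoidable error.

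**Working it through.** The protocol states no hospitalisation rate, cohort size or event count for these endpoints, so there is no planned figure to reproduce. The check is first logical and then illustrative.

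**Step 1: apply the rule to each kind of stay.**

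| Admission | Discharge | Counted under 9.4.2.2 read with 9.2.1? |
|---|---|---|
| before index | before index | no, outside the outcome window |
| before index | on or after index, in follow-up | **yes**, although admission preceded treatment |
| after index | in follow-up | yes, correctly |
| in follow-up | after follow-up ends | no, although admission occurred on treatment |

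No section removes the second row. If the index day itself is not part of follow-up, which the protocol does not say, stays discharged on that day drop out and only those discharged later remain.

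**Step 2: size of the effect at index (assumed values).** Let m be the true mean number of stays per patient in follow-up, equal in both cohorts. Let fA and fB be the shares of Cohorts A and B with a stay that straddles index or ends on it. Then

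ratio of counted stays = (m + fA) / (m + fB), where the true ratio is 1.

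With m = 0.6 and fB = 0.01:

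- fA = 0.02: 0.62 / 0.61 = 1.02
- fA = 0.05: 0.65 / 0.61 = 1.07
- fA = 0.10: 0.70 / 0.61 = 1.15

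Each patient has at most one such stay, so its weight falls as follow-up lengthens or the stay rate rises. With m = 1.2 (for example 0.4 stays a year for 3 years) and the same fB:

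- fA = 0.02: 1.22 / 1.21 = 1.01
- fA = 0.05: 1.25 / 1.21 = 1.03
- fA = 0.10: 1.30 / 1.21 = 1.07

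If fA = fB, the ratio is 1.00 throughout.

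**Step 3: stays open when follow-up ends.** If follow-up ends at a time unrelated to the stay, expected open stays relative to stays in follow-up equal mean length of stay divided by length of follow-up. For assumed mean stays of 5 and 14 days:

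- 1 year: 5 / 365.25 = 1.4% and 14 / 365.25 = 3.8%
- 5 years: 5 / 1826.25 = 0.3% and 14 / 1826.25 = 0.8%

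This loss is small, and nothing in the protocol suggests that it differs much between cohorts.

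**The case against.** **The affected set is narrow.** This stands. Section 9.2 lists drugs only under pharmaceutical claims and none under hospital care, so a drug started on the ward is not shown to create an index date. The realistic cases are mainly prescriptions dated on the discharge day or shortly before it. Whether the index day counts as follow-up is a convention that an analysis plan could settle. That convention would not deal with a stay discharged after index, because the event date would still be the discharge.

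**The direction is unknown.** This also stands. A reader might infer that the rule biases the result against opioids. The documents do not support that: Cohort B includes metamizole and NSAIDs, which may also be started at discharge, and the propensity score in 9.3.1 includes the number of procedures, which may partly balance recent hospital care.

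**Stays lost at a treatment switch.** A reader might add that Cohort B loses stays that end with a switch to an opioid. Section 9.1 does end exposure when a patient "changed treatment group (from opioids to other pain medication or vice versa"), but the censoring list that 9.4.2.2 gives for the hospitalisation rate omits switching. The loss would also need a switch prescription dated before discharge, within the stay. The text does not support building this into the estimate.

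**Fatal stays.** Nor can one say that a stay ending in death is always counted: follow-up may already have ended before the death.

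**A false-positive rate for patients with any stay.** The discharge rule is explicit for the count and for the misuse stay. It reaches the proportion or rate of patients with at least one stay only by extension, and no cohort size is given. A false-positive rate for that measure would rest on neither a stated rule nor a stated sample size.

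**The misuse window.** Read alone, the fixed 2013 to 2017 window would admit misuse stays that ended before index. The general outcome window in 9.2.1 excludes them, so this is a wording gap and not a second error.

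**Discharge dating has a merit.** Length of stay and principal diagnosis are complete for every counted stay. That is true, and it is the price of the change proposed below.

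**Conclusion.** The point holds in a limited form. The protocol fixes a dating rule that counts stays begun before treatment as outcomes of treatment, although the admission date is available and the objective concerns admissions. This goes beyond a detail left open, because the rule is stated and gives the wrong time order for a definable set of stays.

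The size cannot be derived from the documents. Under the assumptions shown (0.6 true stays per patient in each cohort, 1% of Cohort B affected), the counted ratio would be 1.02 to 1.15 if 2% to 10% of Cohort A were affected, 1.01 to 1.07 at 1.2 stays per patient, and 1.00 if the cohorts were equally affected. The loss of stays open at the end of follow-up is a minor second effect. The number of hospitalisations, length of stay and the misuse or addiction stay are concerned; the primary endpoint, death, is not.

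**What to change.** In 9.4.2.2, define a hospitalisation by its admission date and apply the same rule to the misuse or addiction stay:

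- Count a stay if the admission is after the index date and on or before the end of follow-up.
- Assign a stay in progress at index to the baseline period.
- Continue to read the principal diagnosis at discharge.
- Measure length of stay from admission and cut it at the end of follow-up.
- Replace the calendar window for the misuse stay with the patient's own follow-up, and say that the hospitalisation rate uses the same dating.

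The cost is one changed date field in the extraction and a few sentences in the protocol. The downside is small: a few stays open at the data cut will have a truncated length or no discharge diagnosis.
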